3.2 Primary Study Endpoints

Primary (hemodynamic) efficacy outcome variables

SD of systolic BP variability (daytime)

Highest systolic BP 24-h

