1.1 Background

The study objective is to determine whether carbidopa (Lodosyn®) is safe and tolerable in patients with familial dysautonomia (FD), and to learn whether it can inhibit catecholamine-induced paroxysmal hypertension and reduce their exaggerated blood pressure (BP) variability. FD is a brutal genetic disease caused by a developmental defect in primary sensory neurons. The nerves that relay information from arterial baroreceptors are particularly affected resulting in unstable BP. Even mild anxiety can trigger a pronounced release of catecholamines causing paroxysmal hypertension and tachycardia. The subsequent exaggerated BP variability correlates closely with target organ damage in FD. Current drug treatments have little efficacy or intolerable side effects, and none specifically targets BP variability. Carbidopa is a reversible competitive inhibitor of aromatic L-amino acid decarboxylase (DOPA-decarboxylase). It cannot cross the blood brain barrier, and only prevents the formation of catecholamines in the periphery. We recently showed that carbidopa reduces the spillover of dopamine into the circulation and decreases the frequency of nausea in FD patients. Preliminary observations suggest that carbidopa may also lessen the exaggerated BP variability by reducing the formation of norepinephrine outside the brain. To follow up on this finding, we propose to conduct a well-powered study to test of the hypothesis that carbidopa might dampen norepinephrine-driven periods of paroxysmal hypertension in FD patients and thus lessen BP variability. We will use a randomized, double blind, 14-week cross over study comparing two doses of carbidopa and placebo. The sample size will be 30 patients with FD, who will act as their own controls across the two active doses and placebo. In random order, patients will receive high dose carbidopa (600 mg/day), low dose carbidopa (300 mg/day) or matching placebo in three separate 4-week treatment periods. We will monitor adverse events and safety/tolerability parameters throughout. The primary efficacy end-point will be the standard deviation of systolic BP variability. To understand the physiological effects of carbidopa we will measure 24-h catecholamine excretion and diurnal and short-term BP variability. If successful, this would be a major therapeutic breakthrough for FD patients, and could serve as the basis for the use of carbidopa in other more common BP disorders with similar pathophysiology.

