1.6.3 Potential benefits

No benefits can be guaranteed nor will they be implied when consent is obtained. Under the conditions of careful bedside monitoring outlined in this proposal, the risk to any subject will be minimized. We consider these risks smaller than the practical and theoretical benefits derived from the information obtained.

There is a potential benefit that carbidopa may reduce blood pressure variability and paroxysmal

hypertension.

2 Study Objectives

Aim 1: To evaluate the safety and tolerability of carbidopa in FD patients with particular emphasis on the orthostatic fall in blood pressure.

Aim 2: As proof of concept, examine the hemodynamic effects of carbidopa and determine its effects on norepinephrine production, BP variability and paroxysmal hypertension.

Aim 3: In a dose finding study, compare the effects of low (300 mg/day) and high (600 mg/day) dose carbidopa blockade vs. placebo on BP variability and paroxysmal hypertension.

3 Study Design

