To ensure consistency between measurements, cuff size will be recorded in the case report forms and the same cuff size will be used throughout. We will standardize the times of the recordings so that the data collection begins and ends at the same time (i.e., is over the same 24-h period; e.g., 9 AM to 9 AM) on each treatment period. Monitors will be calibrated prior to use following the manufacturers guidelines (SpaceLabs, Service Manual). For this study, patients will be fitted with a validated ambulatory blood pressure monitor (90207 monitor, SpaceLabs, Washington, USA) and instructed to go about their daily activities. For in office visits the patients will be instructed to arrive for the appointment still wearing the ambulatory monitor and simultaneous measurements of blood pressure will be obtained with an automated sphygmomanometer during the orthostatic challenge test to recheck the calibration (Colin Pilot, Texas, USA). For televisits the patients will be instructed to keep the ambulatory blood pressure monitor on during the televisit so that blood pressures and heart rates may be obtained under video supervision by the clinician. Recordings will be downloaded at study visits and repeated if the success rate is not adequate (<80%) or office and ambulatory readings differ by more than 20%. Due to afferent baroreceptor dysfunction, the episodes of paroxysmal hypertension in FD occur predictably in response to emotional or cognitive stimuli. Thus, it is the blood pressure instability during the day (when the patient is awake) that is the major contributor to the increased overall variability. 25 Therefore, our primary efficacy endpoint will focus on the change in blood pressure variability during waking hours (determined from the patient's activity log). Since nocturnal BP fall contributes significantly to 24-h variability, and a non-dipping pattern is associated with end-organ target damage, 43 we will look at changes in blood pressure variability during the entire 24-h period independently. We will also evaluate the weighted variability, to look at the influences episodes of paroxysmal hypertension during the nighttime sub-period. Variability in systolic, diastolic and mean blood pressures will be examined independently.

The following variables will be evaluated and each may have different primary determinants.²⁵

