7.2 Statistical Methods

We have a dedicated statistician for this clinical trial ([name], PhD). Our inclusion criteria use a baseline SD of systolic blood pressure variability ≥15 mmHg (2 SD above our age-matched control data [8.7±3 mmHg]). The mean coefficient of variation in 24-h BP readings in patients with FD is 19.1±5 and 99% of FD patients meet the inclusion criteria. Preliminary data shows that treatment with high dose carbidopa (600 mg/day) reduces blood pressure variability (SD of daytime SBP) by 7.0±5.5 mmHg. Power analysis for the primary outcome (reduction in SD of daytime SBP variability) is detailed in table 3. A sample size of 20 achieves 80% power to detect a reduction of 2.5 (or 2.9) from the null hypothesis of no reduction with an estimated standard deviation of 4.4 for the difference in SD at a significance level of 0.05 using a one-sided (or two-sided) one-sample t-test. The minimum detectable differences are all well below the observed reduction of BP fluctuation of 5.1 from our preliminary data. To ensure that the study is well powered, we will choose a sample size of 30 patients. To account for a drop out rate of around 15%, we will enroll 36 patients in the trial. We will examine the sample distribution of SD of daytime SBP, and if it deviates from the normal distribution, we will employ the nonparametric Wilcoxon test for robustness. In addition, to account for potential covariates, such as age, gender, and disease severity, the analysis of (co)variance (ANOVA and ANCOVA) methods will be used to model the repeated measures data.

Table 3: Power Calculation and Sample Size

Minimal detectable difference: SD BP variability high vs. low dose							
Sample size	T-test	T-test					
	One-sided	Two-sided					
20	-2.5	-2.9					
30	-2.0	-2.3					
40	-1.8	-2.0					

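### The primary efficacy claim has no single definition: section 3.2 lists two primary endpoints where other sections name one, the primary contrast differs between sections, sidedness is open, and no success rule is stated.

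*Combined protocol and SAP*

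**What the plan says.** **Endpoint.** Section 3.2 lists two primary efficacy variables: daytime SD of systolic BP and "Highest systolic BP 24-h". Elsewhere there is one:
- Section 1.1: "The primary efficacy end-point will be the standard deviation of systolic BP variability" (the daytime restriction is not stated here).
- Section 6, 24-hour ambulatory monitoring: "our primary efficacy endpoint will focus on the change in blood pressure variability during waking hours".
- Section 7.2: "Power analysis for the primary outcome (reduction in SD of daytime SBP variability) is detailed in table 3".
- The synopsis, under Statistical Methodology, also refers only to SD of daytime SBP.

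**Contrast.** Aim 3 in section 2, and in the same terms in section 1.1, is to "compare the effects of low (300 mg/day) and high (600 mg/day) dose carbidopa blockade vs. placebo on BP variability and paroxysmal hypertension". The Overview in section 1.4 instead assigns the comparison of 600 with 300 mg/day to Aim 3. Table 3 is headed "Minimal detectable difference: SD BP variability high vs. low dose". The text of 7.2 tests a null of no reduction. Section 8.6.1 plans paired comparisons among all three treatments and ranks none.

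**Sidedness.** Section 7.2 sets the test "at a significance level of 0.05 using a one-sided (or two-sided) one-sample t-test". Table 3 carries both columns, and neither is chosen.

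**Success rule.** None is stated, and there is no multiplicity rule or order of testing.

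**The concern.** Three outcomes are foreseeable and have no agreed reading: one listed endpoint succeeds and the other does not; one dose beats placebo and the other does not; the result is significant one-sided but not two-sided. In each case the trial's main claim would be settled after the data are known. Section 1.5 says the dose comparison is meant to inform which doses go into a Phase III trial, so a split by dose is a result the plan should be able to interpret.

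This goes beyond thin detail. The endpoint list in 3.2 and the heading of Table 3 each conflict with text elsewhere in the same protocol.

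**Working it through.** **1. The plan's own figures.** Inputs from 7.2: SD of the within-patient difference 4.4 mmHg, alpha 0.05, power 80%, one-sample (paired) t-test. The detectable difference d solves P(T > t_crit) = 0.80, where T is noncentral t with n−1 df and noncentrality d√n/4.4.

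| n | One-sided: Table 3 / recomputed | Two-sided: Table 3 / recomputed |
|---|---|---|
| 20 | 2.5 / 2.54 | 2.9 / 2.91 |
| 30 | 2.0 / 2.05 | 2.3 / 2.33 |
| 40 | 1.8 / 1.76 | 2.0 / 2.00 |

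The arithmetic is sound. What is unclear is which comparison it describes.

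**2. The contrast, section by section.**

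| Place | Contrast |
|---|---|
| 1.1 and 2, Aim 3 | each dose vs placebo |
| 1.4 Overview, Aim 3 | 600 vs 300 mg/day |
| 7.2 text | reduction vs no reduction |
| 7.2 Table 3 heading | high vs low dose |
| 8.6.1 | all pairs, unranked |

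Table 3 agrees with one statement of Aim 3 and conflicts with the other two.

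**3. Sidedness at n=30.** The standard error is 4.4/√30 = 0.803 mmHg. Critical t on 29 df is 1.699 one-sided and 2.045 two-sided.
- Critical mean reductions: 1.699 × 0.803 = 1.36 and 2.045 × 0.803 = 1.64 mmHg. An observed reduction between these is significant one-sided only.
- If the 5.5 quoted in 7.2 were the SD of the difference (an assumption), the band would be 1.71 to 2.05 mmHg.
- The probability of landing in the band is P(1.699 < T < 2.045), with T noncentral t and noncentrality (true reduction)/0.803. At SD 4.4:

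| True reduction (mmHg) | Significant one-sided only |
|---|---|
| 0 | 2.5% |
| 1.5 | 13% |
| 2.3 | 8.5% |
| 5.1 | about 0 |

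**4. False positives under the null.** Two independent tests at 0.05 would give 1 − 0.95² = 9.75%. Two doses sharing one placebo period have contrasts correlated 0.5 if variances are equal. Simulated paired t-tests at n=30 then give the rates below. The documents give no correlation between the two endpoints, so it is varied from 0 to 0.95.

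| Tests, any one sufficient | Two-sided 0.05, either direction | Two-sided 0.05, favourable only | One-sided 0.05, favourable |
|---|---|---|---|
| One endpoint, two doses | about 9% | 4.5% | about 9% |
| Two endpoints, two doses; correlation 0 | 17% | 9% | 17% |
| Two endpoints, two doses; correlation 0.95 | 12% | 6% | 11% |

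**5. Power at the cited effect.** At n=30 and 5.1 mmHg, two-sided 0.05, power exceeds 99.9% with SD 4.4 and is 99.8% with SD 5.5.

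**6. Which analysis can carry the primary test.** A model with patient, period and treatment pools one residual variance over all three treatment differences. If those variances differ, the pooled value is wrong for dose versus placebo. With assumed difference SDs of 4.4, 4.4 and 3.0 (high–placebo, low–placebo, high–low), the mean variance is (19.36 + 19.36 + 9.00)/3 = 15.9, against a true 19.4 for high–placebo. Simulated on the protocol's three sequences with 10 patients each, two-sided false positives for high versus placebo are about 7.7%; with 5.5, 5.5 and 3.0 they are about 8.9%. Equal SDs give about 5%. A paired analysis of each contrast does not pool and is not exposed to this.

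**The case against.** Most of the protocol points one way on the endpoint. Sections 1.1, 6 and 7.2 and the synopsis all speak of BP variability or its SD; it comes first in 3.2, and it is the only variable with a power calculation. Section 3.2 is the outlier. That is right, and correcting 3.2 would settle the endpoint. It would leave contrast, sidedness and success rule open.

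The Table 3 heading could be a labelling slip, since the text of 7.2 tests for no reduction. That is possible, but the 1.4 Overview gives the same high-versus-low comparison as Aim 3, so a slip in the table does not explain everything.

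This is a single-centre Phase 2 proof-of-concept study with ample power at 5.1 mmHg. This also stands, and it limits the weight of the point: one stated decision rule is needed, not strict error control over every endpoint. The comfort has limits, though. The preliminary BP data described in 1.4 compare pre-treatment with on-carbidopa recordings in six patients, so they say nothing about high versus low dose.

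A reader might infer that the trial runs a 12–17% false-positive risk. The documents do not support that: it requires any one of four tests to count as success, and no section states such a rule. Nor do they support a reading that the study is underpowered, because Table 3 reproduces.

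**Conclusion.** The concern holds and should be fixed. Section 3.2 conflicts with 1.1, 6 and 7.2 on the number of primary endpoints. Aim 3 is stated two ways, with Table 3 following one of them. Sidedness is not chosen, and nothing says what result makes the trial positive.

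The size is moderate. The firmest figure is about 9% for two doses on one endpoint at two-sided 0.05, of which 4.5% is favourable; it assumes equal variances and that either dose would suffice. The four-test range is conditional on an unstated rule and an assumed endpoint correlation. The sidedness split matters for true reductions around 1.5 to 2.3 mmHg and vanishes at 5.1. The consequence is for error control and interpretation, not for power at the hoped-for effect.

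The choice of analysis population, the criterion for non-normality behind the Wilcoxon fallback, and the look at 15 completers are separate matters and form no part of this conclusion.

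**What to change.** 1. In 3.2, make daytime SD of SBP the sole primary endpoint and move highest 24-h SBP to key secondary. State the daytime restriction in 1.1 so that it matches 6 and 7.2.
2. Fix two-sided 0.05 in 7.2.
3. Name dose versus placebo as the primary contrast, tested in a stated order, for example high dose first and low dose only if the first test succeeds. Define success as the first test being significant in favour of carbidopa. This is an order of testing and implies nothing about which dose is preferable.
4. Reconcile Aim 3 in the 1.4 Overview with 1.1 and 2. Relabel Table 3 to the contrast actually powered. Report high versus low dose as an estimate with a 95% CI.
5. Keep a paired analysis of each contrast as the primary test, which is what 7.2 powers. Any mixed model should not assume equal variances for the three treatment differences.

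**Cost.** Wording only, with no added patients or procedures. Under the ordered test the high-dose comparison keeps the full 0.05, so its two-sided detectable difference at n=30 stays at 2.33 mmHg (SD 4.4). Splitting alpha equally over four tests (0.0125 each) would raise it to 2.84 mmHg. The real downside is that highest SBP loses primary status and a low-dose claim becomes conditional on the high-dose result.

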3.3 Secondary Study Endpoints

Secondary efficacy outcome variables

- 24-h Urinary norepinephrine excretion
- CV of systolic BP variability (daytime)
- Weighted SD of BP variability
- Percent/number of systolic readings >140 mmHg in 24-h
- Maximum hypertensive peak produced by Stroop test (cognitive arousal) or hear rate during congnitive stimulation while performing serial sevens testing
- Short-term beat-to-beat spontaneous SD of BP or heart rate (5-minutes) breathing spontaneous
- Morning surge in systolic BP on awakening from sleep (24-h)

3.4 Primary Safety Endpoints

Safety measures

- Adverse events
- Laboratory values
 CBC

 - Metabolic panel
- Urinalysis
- Vital signs
- Body temperature
- Weight
- Blood pressure (sitting and standing)
- ECG (at screening and termination visit)

Tolerability measures

- Number of subjects (%) who discontinue the study
- Number of subjects (%) who discontinue the study due to AEs.
- Severity of hypotension during an active stand test
- Lowest systolic BP (24-h)
- Worsening in OH-Q scores
- Frequency of symptoms noted in their diary

4 Subject Selection and Withdrawal

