Benzodiazepines (like diazepam and clonazepam ¹¹) are effective anxiolytics and frequently lower blood pressure during a prolonged anxiety-induced paroxysmal hypertensive attack. Many patients, however, quickly become tolerant and require increasing doses, ^{7,13} which can cause severe respiratory depression as patient also lack inputs from chemoreceptors. ¹⁸ The central sympatholytic agent clonidine has been used with some success, ¹¹ but its use is limited by the unwanted side effects of sedation, hypotension and rebound hypertension. Beta-blockers and ACE-inhibitors frequently produce hypokalemia. Vasodilators like calcium channel blockers, hydralazine and nitrates frequently worsen orthostatic hypotension.

Dopa-Decarboxylase-Inhibition and Blood Pressure Variability:

At rest, carbidopa does not have profound effects on tissue concentrations of norepinephrine³³ or on blood pressure.³⁶ In patients with classic (efferent) autonomic failure, carbidopa does not worsen orthostatic hypotension.³⁷ Most relevant to this proposal, experimental data shows that at times of emotional arousal, when rates of catecholamines synthesis increase, carbidopa effectively blocks the additional production of dopamine, norepinephrine and epinephrine.³³ Animal data shows that the suppression of norepinephrine synthesis in sympathetic nerves is even more effective at larger doses.³⁸ If carbidopa had the same effect in patients with FD, inhibiting catecholamine surges at times of arousal would help dampen paroxysmal hypertensive peaks and should subsequently reduce overall variability. Since carbidopa itself cannot cross the blood brain barrier, ¹² even at high doses, ^{36,39} it has no effects on the CNS, thus making it a viable alternative to benzodiazepines and clonidine for the treatment of catecholamine-induced paroxysmal hypertension in FD. Its effects on the severity of orthostatic hypotension in patients with FD are not clear and warrant further investigation to ensure the drug is safe.¹³

C: Preliminary Data

Recently, in a double-bind, placebo-controlled trial sponsored by the FDA's Office of Orphan Products Development ¹³ we showed the short-term safety of carbidopa and its antiemetic efficacy in patients with FD. Carbidopa successfully lessened the nausea/retching/vomiting episodes and reduced the need for benzodiazepines.¹³ Preliminary results show carbidopa also has a beneficial effect on stabilizing the blood pressure and reducing its variability.

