Average blood pressures: The theoretical underlying level of blood pressure calculated by averaging several blood pressure values collected over the defined time periods (entire recording, sleep hours, wake hours).

Standard Deviation: The variability in blood pressure overtime determined by the standard deviation (entire recording sleep hours, wake hours).

Coefficient of Variation: The measurement of blood pressure variability based on the standard deviation that also takes into account the underlying level of BP. Calculated as follows: CV = [SD/mean BP] x 100.

Nighttime Dipping: Analysis of the circadian pattern based on the difference in average daytime and nighttime values and expressed as a percentage. With normal night-time "dipping" defined as a 10% fall in BP during sleeping hours.⁴³

Weighted Standard Deviation: Using a "weighted" measurement of standard deviation of 24-h ambulatory BP that avoids the contribution of nocturnal dipping to the overall variability, but still includes the BP variability during the night has been suggested as an accurate measurement of cardiovascular risk.²³ Calculated as follows: wSD = [daytime SD x14 + nighttime SD x6]/20).

Morning Surge in Blood Pressure: The increase in blood pressure that occurs on awakening from sleep and is exaggerated in patients with FD. The morning surge will be calculated as the difference between the mean

Version: 5.0 (date Echruany 12, 2019)

Version: 5.0 (date February 12, 2018)

systolic blood pressure during the hour that included the lowest blood pressure during sleep and maximum value detected within 2-h of awakening from sleep (as previously described¹⁰)

Page 18

Abbreviations: BP, blood pressure; SD, standard deviation; CV, coefficient of variation. wSD, weighted standard deviation.

Questionnaires:

Patients will complete 2-questionnaires to assess tolerability.

OH-Q: The orthostatic hypotension questionnaire (abbreviated to OH-Q) was recently validated and consists of 10-items graded on an 11-point scale (0 to 10).⁴² Six items assess symptoms of neurogenic OH and 4 address the impact they have on activities of daily living (Appendix 1).

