Symptom Diary: As we did in our previous trial, ¹³ we will use a tailored questionnaire to examine symptoms over the treatment period and the used of as needed medications. Each day will have a designated page. Since nausea/vomiting and hypertension occur together in FD we will use a diary consisting of a simplified version of the Rhodes Index ⁴⁴ symptoms of nausea/retching, with items addressing vomiting/throwing up omitted, as most participants will have had anti-reflux surgery to prevent vomiting (fundoplication), graded on a 5-point scale (appendix 2). The diary will also include space to write down any adverse events on a daily basis.

Catecholamines:

Prior to arriving for a study visit or performing a televisit, patients will be asked to collect a 24-hour urine sample in a bottle shielded from light containing preservative. Patients will be instructed to refrigerate their sample and bring it on the morning of their visit in a cool bag or provided with a prescription to take it to a local laboratory. Catecholamines will be measured using high-pressure liquid chromatography as previously described. 45 Because urine catecholamine collections reflect periods of sympathetic nerve activation over an entire day, in this particular circumstance urinary excretion will more clinically useful information, than a plasma "snap-shot" obtained from a blood draw at the office, which has the emotional component of a having and IV inserted in the arm (which despite not feeling pain, is not well tolerated by these patients).

Autonomic Testing:

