We are interested in how the low blood pressure symptoms that you experiences affect daily life. Please rate each item by ticking the number that best represents how much on the average the activity has been interfered with over the past week by the low blood pressure symptoms you have experienced. If you cannot do the activity for reasons other than low blood pressure, please check the box at right.									
			☐ Cannot do for other						
1. Activities that red	quire standing f	or a short time	reasons						
No 0	No 0 1 2 3 4 5 6 7 8 9 10 Complete								
interference			│						
	☐ Cannot do for other								
2. Activities that red	quire standing for	or a long time	2. Activities that require standing for a long time reasons						
	1 2 3								
	1 2 3								
No 0	1 2 3		9 10 Complete						
No 0 interference	1 2 3		9 10 Complete						
No 0 interference		4 5 6 7 8	9 10 Complete interference						
No 0 interference		4 5 6 7 8	9 10 Complete interference Cannot do for other reasons						
No 0 interference 3. Activities that red	quire walking fo	r a short time	9 10 Complete interference Cannot do for other reasons						
No 0 interference 3. Activities that rec	quire walking fo	r a short time	9 10 Complete interference Cannot do for other reasons 9 10 Complete						
No 0 interference 3. Activities that rec	quire walking fo	r a short time	9 10 Complete interference Cannot do for other reasons 9 10 Complete						
No 0 interference 3. Activities that rec	quire walking fo	r a short time 4	9 10 Complete interference Cannot do for other reasons 9 10 Complete interference						
No 0 interference	quire walking fo	r a short time 4	9 10 Complete interference Cannot do for other reasons 9 10 Complete interference Cannot do for other						

SYMPTOM DIAR	Y					
Name (last, first	t):					
Current dat	-		Time:			
Retching is the effor Please mark the bo Please make only o	x in each rov	w that most o		ponds to you	ır experience	-
In the last 24 hours, I have felt nauseated or sick to my stomach	Not at all	1-hour or less	2-3 hours	4-6 hours	More than 6 hours	
In the last 24 hours, from nausea/sickness, I have felt "" distress	No	Mild	Moderate	Great	Severe	
In the last 24 hours, I have had periods of retching.	No	1 – 2 hours	3 – 4 hours	5 – 6 hours	7 or more	
What time of day was the worst?						
Did you miss school or work?	□ No □ Yes					
Did you take something for your nausea today?	□ No □ Yes	 3				
Did you take something for your blood pressure today?	□ No □ Yes					

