Did you have anything else that bothered you today (an Adverse Event)?						

Diary Day: 1 of 28

Sample Instructions for Testing/Dose administration:

Dov	Instructions
Day	Instructions
Apr 1st The day before your visit	At 9 AM fit the BP cuff to your < <left>> arm (<<6>> cm above your elbow). Turn the monitor on, start the recording by pressing the blue button, go about your daily activities. Fill in the diary your meal times, times you took medications and the time you go to sleep and wake up. Starting this same morning, discard your first morning urine. For the next 24-h collect your urine in the container provided. Write here when you started the collection. START TIME: AM You should continue to take your study medication every 6-hours.</left>
Apr 2nd The day of your visit	Your appointment or televisit at the Dysautonomia Clinic is scheduled for <<10:00>> AM. Finish your urine collection the same time you started it the previous day. Be sure this time to include your first early morning urine sample after waking up. Write here when you ended the collection: END TIME: AM Take your first morning dose of study medication at <<8:00>> AM. Write down here the exact time you took your medication. MEDICATION TIMING: AM Come into the clinic for your study visit. At 11 AM we will perform your autonomic function tests in the office of via telemedicine. DO NOT take off your BP monitor yet, will take it off when you arrive at the clinic. Here is a check list with things to bring with you to the clinic or have prepared for the televisit: Your symptom diary Your 24-h urine collection The blood pressure monitor (which you should be still wearing) All your unused medication After your visit: So that you do not stop your dose too quickly, we will reduce your current dose slowly. At the end of this visit, we will give you 2 bottles of medication. One bottle will be marked with todays and tomorrows dates, and will contain 2 of the same pills that you have been taking. One bottle will contain more pills. These pills are your next treatment, and you should not start taking them yet. You will take one-pill from the bottle with today and tomorrows date. Once you have taken this pill, do not take any more pills for the rest of the day.
Apr 3rd The day after your visit	IN THE AFTERNOON, TAKE ONE PILL FROM THE BOTTLE MARKED WITH TODAY'S DATE. Do not take any more medication for the rest of the day Apr 2: Take 1 pill Apr 3: Take 1

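### The diary tolerability measure rests on nausea and retching, which carbidopa is expected to relieve; orthostatic symptoms reach it only through the open adverse event line

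*Combined protocol and SAP*

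**What the plan says.** Section 3.4 gives six tolerability measures, the last of which is "Frequency of symptoms noted in their diary". Section 6 (Questionnaires) assigns both the OH-Q and the diary to the same purpose: "Patients will complete 2-questionnaires to assess tolerability".

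The same part of section 6 explains the diary's content: "Since nausea/vomiting and hypertension occur together in FD we will use a diary consisting of a simplified version of the Rhodes Index". It describes the items as "symptoms of nausea/retching, with items addressing vomiting/throwing up omitted".

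The form in the Appendix carries this out. One graded item begins "In the last 24 hours, I have felt nauseated or sick to my stomach", a second grades the distress this caused, and a third reads "In the last 24 hours, I have had periods of retching". The form also asks for the worst time of day, missed school or work, and whether anything was taken for nausea or for blood pressure. Any other complaint goes under an open prompt that starts "Did you have anything else that bothered you today (an Adverse Event".

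Section 1.4, on the earlier placebo-controlled trial in the same disease, states: "Carbidopa successfully lessened the nausea/retching/vomiting episodes and reduced the need for benzodiazepines". Sections 1.1 and 1.4 thus both present relief of nausea as a known effect of the drug. Nausea and retching appear in neither efficacy list (3.2 and 3.3).

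**The concern.** A tolerability measure should respond to what the drug may do to the patient. Here the graded symptoms are ones that the protocol expects the drug to improve, and the stated reason for choosing them is that they accompany the hypertension under treatment. They are markers of the disease process, not suspected harms.

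Aim 1 stresses the orthostatic fall in pressure, and section 1.4 says the drug's effect on orthostatic hypotension in these patients is unclear and needs study. The diary is the only patient-reported instrument completed every day, yet it names no orthostatic symptom. If its frequency is tabulated by treatment, a fall in nausea on carbidopa would read as better tolerability. Pooled with other entries, that fall could offset a rise in orthostatic complaints.

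**Working it through.** The plan states no figure for this measure, so there is none to reproduce. The check sets the relevant places side by side and then does two short pieces of arithmetic.

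**1. What the diary can register**

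| Symptom | Daily question | Effect the protocol expects from carbidopa |
|---|---|---|
| Nausea, hours | Graded item | Reduction (1.1, 1.4) |
| Nausea, distress | Graded item | Reduction (1.4) |
| Retching | Graded item | Reduction (1.4) |
| Dizziness, faintness, falls on standing | Open prompt only | Unclear; the stress of Aim 1 |

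All three graded symptom items belong to the first group. The remaining structured items (school or work, medication) are not symptoms.

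**2. How the count behaves**

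Neither 3.4 nor section 7 says whether frequency means days, episodes or graded hours, or whether symptoms are pooled. Suppose they are pooled as symptom-days: C = N + O, where N is nausea/retching days and O is days with another complaint on the open line. The drug-minus-placebo difference is then ΔC = ΔN + ΔO. A rise in O is hidden whenever the fall in N is at least as large. The documents give no value for N or O in either condition, so ΔC cannot be computed.

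Illustration only, with every rate assumed. Take 28-day periods. Nausea occurs on 30% of placebo days (28 × 0.30 = 8.4) and 20% of drug days (28 × 0.20 = 5.6). Dizziness occurs on 10% (2.8) and 20% (5.6). Let c be the share of dizziness days that the patient writes on the open line.

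- c = 0: 8.4 against 5.6, so 2.8/8.4 = 33% fewer symptom-days on drug.
- c = 0.5: 8.4 + 1.4 = 9.8 against 5.6 + 2.8 = 8.4, so 1.4/9.8 = 14% fewer.
- c = 1: 8.4 + 2.8 = 11.2 against 5.6 + 5.6 = 11.2, no difference.
- c = 1 with no nausea benefit: 11.2 against 8.4 + 5.6 = 14.0, so 2.8/11.2 = 25% more.

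The result runs from a marked apparent advantage to a visible harm, depending on inputs the documents do not supply. The direction of the distortion follows from the diary's content. Its size does not.

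**3. Structured orthostatic questions elsewhere**

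The OH-Q is completed at visits and asks for an average over the past week (Appendix). Each treatment period lasts 28 days (1.1, 1.4).

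- Covered: 7/28 = 25%.
- Not covered by a structured orthostatic symptom question: 21/28 = 75%, including the first weeks on a new treatment.

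If the 14-day visit window in the Fig. 7 legend changed a period's length in full (an assumption), coverage would run from 7/42 = 17% to 7/14 = 50%. The stand test and the 24-h recording fall at the end of each period. Outside the recall week, orthostatic symptoms are picked up by the open diary prompt and the adverse event calls.

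**The case against.** The strongest reply is that the diary is one tolerability measure of six, and three of the others address hypotension directly: the active stand test, the lowest 24-h systolic pressure, and worsening on the OH-Q. Sitting and standing pressures are also safety measures. Patients are called on the day a new treatment starts, at day 7 and weekly thereafter. Section 8.2 requires specific questioning about adverse events at every contact, and the diary itself prompts daily for anything else that was bothersome. A dizzy spell written there is a symptom noted in the diary. All of this stands.

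A reader might go further and infer that the plan scores a benefit as good tolerability, that daily orthostatic symptoms go unasked, or that Aim 1 as a whole will be answered with bias. The documents do not support these readings. There is no scoring or pooling rule, and section 8.6.1 says only that end-points are first examined descriptively. What the diary lacks is a named orthostatic item, not any daily prompt. The other measures were chosen to detect the harm in question.

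Nor can a particular percentage be attached. The nausea benefit comes from an earlier trial of 12 patients, and this trial selects on unstable blood pressure, not on nausea.

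It is also fair to object to removing nausea from view. New or worse nausea on an oral drug is a legitimate tolerability finding, and dropping the items could hide it. That objection is accepted and shapes the remedy.

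What survives is narrower. The diary component, read as 3.4 lists it, is dominated by symptoms the drug is expected to relieve, and its view of orthostatic symptoms depends on unprompted free text.

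**Conclusion.** The point holds for the diary component only. That component would largely reflect an expected benefit and is a weak instrument for the harm Aim 1 stresses; on its own it cannot support a statement about tolerability. Orthostatic tolerability as a whole is still measured by other means.

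This conclusion assumes that the graded items are counted as 3.4 lists them and that some nausea benefit carries over from the earlier trial. The one quantity the documents yield is the 25% of each period within OH-Q recall. This is a cheap improvement, not a flaw that undermines the trial.

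**What to change.** In section 3.4 and section 6 (Questionnaires):

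- Report the nausea and retching scores by treatment as a separate outcome, read in either direction. Do not pool them with other diary symptoms as evidence of tolerability.
- Add one daily yes/no row to the diary on dizziness, fainting or a fall on standing.
- Define the diary's tolerability measure as the share of diary days with a yes on that row, by treatment, presented with the entries on the adverse event line.

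The separate reporting needs no new data and should be written down before treatment codes are opened for analysis. The row adds one line to an existing page. Its cost is incomplete history: patients already enrolled will lack it for some or all periods, and the documents do not say how many they are. It should therefore be summarised only in patients who have it for every period being compared, with that number stated.
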